Research Protocol

Using mental imagination to prevent excessive gestational weight gain in overweight and obese pregnant women

I. Objectives

1. To determine feasibility of the goal-oriented intervention: recruitment, randomization, retention, and intervention implementation.
2. To investigate the potential efficacy of the intervention on gestational weight gain (primary outcome) and maternal and birth outcomes (secondary outcomes: gestational diabetes, gestational hypertension, mode of delivery, length of labor, apgar score, new born body weight, and premature baby).

Primary hypothesis. A higher proportion of intervention participants will have healthy gestational weight gain than the usual prenatal care participants

Secondary hypothesis. A lower proportion of intervention participants will have gestational diabetes, gestational hypertension, cesarean delivery, premature birth, longer duration of labor, unhealthy birth weight (>4000 or < 2500 grams), premature birth, and APPGAR score ≤ 3 than the usual prenatal care participants.

3. To investigate the potential impact of the intervention on lifestyle behaviors: diet (caloric, fat, sugary drink, fruit and vegetable intakes) and physical activity (walking steps and energy expenditure).

Hypothesis 1. A higher proportion of intervention participants will eat healthier than the usual prenatal care participants.

Hypothesis 2. A higher proportion of intervention participants will have more walking steps and higher energy expenditure than the usual prenatal care participants.

4. To investigate the potential intervention effects on motivation (autonomous motivation, self-efficacy, consideration of future, happiness, and hope), emotion (emotion control, stress, and depressive symptoms), cognition (executive function and impulsiveness) and psychological eating (cognitive restraint eating, emotional eating, overeating and eating out of boredom)

Hypothesis 1. A higher proportion of intervention participants will have higher motivation and self-efficacy, better emotion, higher cognition, and lower psychological eating than the usual prenatal care participants.

[figure not shown]
II. Background and Rationale

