A.1. Overweight or obese pregnant women. Nearly 56% of American women aged 20-39 are overweight or obese.¹ These women are at least two times more likely than normal weight women (65-85% for overweight or obese vs. 34% for normal weight) to experience excessive gestational weight gain (EGWG),²⁻⁸ exceeding Institute of Medicine (IOM) pregnancy weight gain guidelines.⁹ EGGW is a serious public health problem because it negatively influences maternal and birth outcomes: gestational diabetes,¹⁰ gestational hypertension,¹¹ cesarean delivery,¹² and fetal macrosomia (birth weight > 4000 gm).^{12,13} EGGW is also a strong predictor of significant postpartum weight retention (retaining ≥ 10 lbs), which is associated with lifelong obesity in mothers¹⁴ and childhood obesity.^{15,16} Pregnancy is a teachable movement for weight management and obesity prevention.¹⁷ Therefore, it is imperative to help overweight or obese pregnant women prevent EGGW.

A.2. Previous lifestyle behavior intervention studies. Healthy lifestyle behaviors (healthy eating and physical activity, **PA**) can prevent EGWG in overweight or obese pregnant women.¹⁸⁻²⁸ Efficacious strategies identified in prior studies involve personalized caloric restriction,²¹⁻²⁵ frequent in-person meeting attendance²²⁻²⁴ or phone counseling^{25,26} and frequent text messages requiring responses.²⁶ Such interventions have limited practicality, scalability, and sustainability due to high participant burden and excessive cost for clinical practice. Also, adherence was problematic,^{22,26,29-31} perhaps because of educational materials and counseling that were prescriptive and not sufficiently flexible or tailored to individuals.³² Moreover, the prior studies paid little or no attention to motivation, emotion and executive function, all of which are crucial for healthy lifestyle behaviors.

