Feasibility. We will use our tracking records to assess recruitment, randomization and retention. To assess intervention implementation, we will extract data from our study web site that will track and capture details about all activities (e.g., amount of and type of activities completed and % of participants used type in box). We will record the attendance of individual coaching session. Intervention participants will report their motivation and barriers preventing them from engaging in the intervention activities and evaluate the usefulness of with each EFT intervention component. We will also use semi-structure interview questions (up to 20 minutes/an individual interview via zoom) to ask participants to evaluate the intervention. We will use website tracking data, individual coaching session, and results of phone interview to revise the intervention contents for a future large scale intervention study.

Primary outcome: GWG (in lbs). Body weight or gestational weight gain will be extracted from participants' electronic health record.

To compute weekly GWG, we will subtract the measured weights between two adjacent time points (T2 vs. T1; T3 vs. T2) then divide by the number of weeks between the two time points. The IOM recommends that overweight women (BMI 25.0-29.9) be limited to total GWG of 15-25 lbs and obese women (BMI ≥ 30.0) to 11-20 lbs.⁹ To compute the total GWG, we will subtract the self-reported pre-pregnancy weight from weight measured at T3. A woman will be identified as having excessive gestational weight gain if her total gestational weight gain exceeds the Institute of Medicine's criteria.

Secondary outcomes: gestational diabetes, gestational hypertension, mode of delivery, length of labor, apgar score, new born body weight, and premature baby will be accessed by [name] (Co-I) or research staff from the participants' electronic health record.

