Recruitment and enrollment. We will use our previously successful strategies¹¹⁹ to get clinical care providers (e.g., Ob/Gyn and Midwives, hereafter providers) at five collaborating OSU prenatal care clinics to refer first trimester pregnant women to the study. Drs. [name] (PI) and [name] (Co-I) will meet with them to present the study purposes and requirements and demonstrate the web-based intervention. Study flyers will be posted in high-traffic and waiting areas at the clinics and in other locations near our study sites, e.g., pediatric clinics. The medical assistants and/or receptionists at each clinic will distribute the study flyer to participants. Potential participants who are interested in the study will ask their providers about the study or the providers will initiate the conversation about the study with the potential participants. Providers will put the potential participants' chart into IHIS Inbox of trained study staff for screening if the potential participants expressed interest in learning more about the study. Next, the trained research staff will log into IHIS to make an initial screening (for example, gestational age based on ultrasound record and body mass index [if available]). If they are potentially qualified to participate, we will perform "an initial contact of potential participants" (Described below).

Initial Contact of Potential Participants - Research staff will contact potential participants by phone to further determine eligibility. We will obtain verbal consent prior to screening and obtaining demographic information. Collecting demographic data will help us revise or plan for recruitment strategies for a future R01. If eligible, participants will provide up to 3 telephone numbers (at least 1 capable of receiving text messages), email address, and physical address as contact information. We will ask if we can leave a message via phone (Yes/No). Next, the Research staff will schedule a zoom meeting (individual information session, described below) within the five business days with the qualified participants. Then, the trained research staff will send the full consent form to the participants for review (via email) prior to the first scheduled zoom meeting. Participants will be informed the zoom meeting will be either audio or video recorded per their preferences.

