complete ≥ 12 weekly intervention activity with $\geq 80\%$ weekly activities completed; 75% of women will be able to generate good quality of steps to achieve their chosen goals; 80% will use the pre-written goals instead of type in (intervention implementation). **Aim 2**, we will first use descriptive statistics and trend plots to summarize and visually compare the weekly gestation weight gain over time. Mixed-effects linear modeling will be used to model the weekly GWG as a linear function of treatment (intervention vs. usual prenatal care care), time, and treatment by time interaction. From the model, we can derive estimates of the time-averaged weekly gestational weight gain for each group, the between-group difference in weekly gestational weight gain at each time point and adjust for within-subject clustering from repeated measures and covariates (e.g., race). We will use logistic regression to estimate the between-group (intervention vs. usual care) difference in the probability of having a binary outcome (for example, excessive gestational weight gain, gestational hypertension, new born body weight), adjusting for covariates (e.g., race). **Aims 3 and 4**, mixed-effects linear modeling will be used to model each continuous outcome (dietary intakes, PA, and psychological eating for Aim 3; motivation, emotion and cognition for Aim 4) as a linear function of treatment, time, and the treatment by time interaction. The intervention effects will be estimated by between-group comparisons of change in the outcome (e.g., healthy lifestyle behaviors) from baseline. Again, we will adjust for within-subject clustering from repeated measures and covariates (e.g., race) in the mixed-effects regression models. **Missing data**. We will carefully examine the pattern of missing data and conduct appropriate multiple imputation if missing at random is indicated. The mixed-effects modeling allows for missing at random. If missing not at random exists, pattern mixture modeling will be used. Sensitivity analysis will evaluate the robustness of study findings without multiple imputation vs. those with imputation or from pattern-mixture modeling.

Zoom IRB Boilerplate:

Zoom is a secure, user-friendly, cloud-based enterprise videoconferencing service that Ohio State University implemented in 2018. Zoom is accessible to faculty and staff at all Ohio State campuses via <https://carmenzoom.osu.edu> .

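### The only inferential analysis specified for newborn weight is logistic regression of one yes/no outcome that pools both weight extremes and ignores gestational age, so a shift in weight can be hidden or appear reversed

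*Combined protocol and SAP*

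**What the plan says.** The secondary hypothesis in section I expects fewer intervention participants to have "unhealthy birth weight (>4000 or < 2500 grams), premature birth, and APPGAR score ≤ 3". One label therefore covers both ends of the weight scale, and premature birth is a separate item in the same sentence.

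The Aim 2 paragraph of section F assigns logistic regression to binary outcomes and lists "excessive gestational weight gain, gestational hypertension, new born body weight" as examples. Race is the only covariate named there, and it too is given as an example. That sentence carries no cut-offs; they come from section I. The linear mixed models of section F cover weekly gestational weight gain under Aim 2 and, for Aims 3 and 4, will "model each continuous outcome (dietary intakes, PA, and psychological eating for Aim 3; motivation, emotion and cognition for Aim 4"). Newborn weight is in neither list.

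In section C the secondary outcomes, including "new born body weight, and premature baby will be accessed by" study staff, come from the electronic health record. Recruitment screening in section D uses "gestational age based on ultrasound record". The background singles out the upper end, "fetal macrosomia (birth weight > 4000 gm"), and the conceptual framework names macrosomia as a key outcome. No z-score and no small- or large-for-gestational-age measure is defined anywhere.

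**The concern.** Three features of the planned outcome make it a weak measure of what the intervention does to newborn weight.

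1. **Opposite tails in one outcome.** If limiting maternal gain moves the weight distribution down, births above 4000 g become fewer and births below 2500 g more frequent. The pooled rate records only the net change, which may be near zero or go the wrong way while macrosomia falls.
2. **No account of gestational age.** A weight in grams reflects length of gestation as well as growth. The plan predicts fewer premature births, and that alone would change how many babies fall below 2500 g.
3. **Loss of information.** Two cut-offs applied to several dozen births leave few events.

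The sample size paragraph in section B says that point estimates, effect sizes and 95% confidence intervals will guide the full-scale trial. An odds ratio for the pooled outcome would be a poor guide for newborn weight.

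**Working it through.** **The plan's own power figure.** The plan states power for weekly weight gain only: 36 per group, difference 0.33 lb, SD 0.55 lb, correlation 0.7 between two measures, two-sided 0.05. The SD of the average of two measures is 0.55 × √((1 + 0.7)/2) = 0.507. The standard error is 0.507 × √(2/36) = 0.1195. Power is Φ(0.33/0.1195 − 1.96) = Φ(0.80) = 78.8%, against the stated 80%. It reproduces within rounding, shows no error and does not bear on newborn weight.

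**Inputs for newborn weight.** The cut-offs come from section I. The 36 per arm is borrowed from the weight-gain calculation in section B. Everything else is assumed: a normal distribution, usual-care mean 3300-3500 g, SD 450-600 g, and a downward shift of 200 g with the SD unchanged.

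**Pooled tails.** The upper tail is 1 − Φ((4000 − mean)/SD) and the lower tail is Φ((2500 − mean)/SD). At mean 3400 g and SD 500 g these are 1 − Φ(1.2) = 11.5% and Φ(−1.8) = 3.6%. After the shift they are 1 − Φ(1.6) = 5.5% and Φ(−1.4) = 8.1%.

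| Usual-care mean (SD 500 g) | Above 4000 g | Below 2500 g | Pooled |
|---|---|---|---|
| 3300 g | 8.1% → 3.6% | 5.5% → 11.5% | 13.6% → 15.1% |
| 3400 g | 11.5% → 5.5% | 3.6% → 8.1% | 15.1% → 13.6% |
| 3500 g | 15.9% → 8.1% | 2.3% → 5.5% | 18.1% → 13.6% |

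At 3300 g the pooled outcome goes against the intervention while macrosomia falls by more than half. At 3400 g about 10 pooled events are expected in all: 36 × (0.151 + 0.136) = 10.3.

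**Power for the 200 g shift.** Normal approximation, 36 per arm. At mean 3400 g and SD 500 g it is 40% for the continuous value, 15% for above 4000 g alone and about 4% for the pooled outcome. Over all the means and SDs it is 29-47%, 12-18% and 3-9%. These count rejection in the direction of the true difference only, which has probability 2.5% when there is no difference, so 4% is barely above chance.

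**Power by shift in SD units.** The continuous comparison uses a noncentral t with 70 df and noncentrality shift × √18. The binary comparison assumes 12% above 4000 g in usual care, with the intervention rate found by moving the normal distribution down.

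| Shift | Continuous | Above 4000 g alone |
|---|---|---|
| 0.3 SD | 24% | 12% v 7.0%: 11% |
| 0.4 SD | 39% | 12% v 5.8%: 15% |
| 0.5 SD | 55% | 12% v 4.7%: 20% |

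**Information kept.** For a small shift, efficiency relative to the continuous analysis is (change in event probability per SD of shift)² / [p(1 − p)]. At mean 3400 g and SD 500 g:
- above 4000 g: 0.1942² / (0.1151 × 0.8849) = 0.37
- below 2500 g: 0.0790² / (0.0359 × 0.9641) = 0.18
- pooled: (0.1942 − 0.0790)² / (0.1510 × 0.8490) = 0.10

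Over all the means and SDs the ranges are 25-49%, 9-33% and 1-26%. More than half is lost in every case.

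**Overlap with premature birth.** With preterm rate q, and proportions a of preterm and b of term babies below 2500 g, the preterm share of the low tail is qa / (qa + (1 − q)b). For q = 8-15%, a = 40-60% and b = 1.5-4%, the extremes are 0.032/(0.032 + 0.0368) = 47% and 0.090/(0.090 + 0.01275) = 88%. None of these rates is in the documents.

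**The case against.** The plan's hypothesis concerns a proportion with unhealthy birth weight, and logistic regression of a proportion answers it. The cut-offs have clinical meaning. A reader might infer that the trial asks whether limiting maternal gain changes fetal growth, and that the plan fails to answer its own question. The documents do not support this: growth for gestational age is not a stated aim. That part of the objection stands, and it argues for adding an analysis rather than replacing the outcome.

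A reader might also infer that the continuous weights are thrown away. They are extracted from the record, section F plans descriptive statistics, section B promises effect sizes and intervals, and both the outcome examples and the covariates in the Aim 2 sentence are open lists. A summary in grams is not excluded. What remains is that no continuous or gestational-age-standardised comparison is specified.

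The power figures have limits:
- They are for raw weight, not for a z-score, whose SD and effect size may differ.
- The normal approximation is rough with about 4 against 2 to 3 expected events per arm.
- The 36 per arm is the number left after attrition for weight gain, and birth records may be available for more women. At 45 per arm (mean 3400 g, SD 500 g, 200 g shift) power is 48% continuous, 17% above 4000 g and 4% pooled, so the comparison does not change.

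Finally, this is one of seven secondary outcomes in a pilot that says it is not powered below 0.6 SD. Neither analysis would be confirmatory. That limits the weight of the point, but a pilot meant to supply estimates gains most from the more informative one.

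**Conclusion.** The point holds as a weakness of a secondary analysis. The only inferential analysis specified for newborn weight is a pooled yes/no outcome at fixed gram limits, without regard to gestational age. This is read directly from sections I and F.

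That opposite tails offset each other under a downward shift follows from the definition. The size depends on the assumed distribution: a 200 g shift at SD 500 g changes the pooled rate by 1.5 percentage points in either direction for means of 3300-3400 g, and by 4.5 points at 3500 g, where the upper tail dominates. The loss of more than half of the information held for every distribution tried, but all of them are assumptions.

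A reader might go further and say that the low end mostly recounts premature birth. The documents do not support that as a fact. Overlap is to be expected, since premature birth is counted separately, and it may be large, but the 47-88% range rests wholly on rates from outside the documents.

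**What to change.** In the Aim 2 paragraph of section F:

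1. Keep the section I cut-offs, but report births above 4000 g and below 2500 g separately by arm.
2. Add a linear regression of birth-weight-for-gestational-age z-score on treatment and race, reporting the mean difference and 95% CI. Name the reference chart in advance.
3. Use gestational age at delivery to build the z-score rather than as a covariate, because it is determined after randomisation.

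No new visit is needed. Birth weight is already extracted from the health record, and the premature-birth outcome already requires gestational age at delivery.

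The cost is one more secondary analysis, the choice of a chart, and a result in SD units rather than grams. Power stays modest, so the estimate serves planning of the full-scale trial rather than a confirmatory test.

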Inclusion criteria. Participants must be pregnant women ≤ 13 week-gestation with a single fetus as assessed by ultrasound (Research staff or [name], Co-I, a board-certified Ob/Gyn at a collaborating clinic will verify eligibility from the patient's Electronic Health Record, EHR). Participants must also have self-reported (1) pre-pregnancy body mass index (BMI) of 25.0-45.0 kg/m² and height (we will use height and weight to compute body mass index). (2) ability to read and speak English, (3) age of 18-45 years, (4) access to a working smart phone with unlimited text messaging (89 to 94% of American adults aged 18 to 49 years own a smart phone)⁹⁷ and access to internet and (5) receipt of prenatal care and from our collaborating clinics and plan to deliver the baby at The Ohio State University (OSU) Wexner Medical Center, 6) a resident of Franklin Count, and (7) committed to the 20-week intervention.

Exclusion criteria. Self-reported (1) history of ≥ 3 miscarriages, (2) planned termination of the pregnancy, (3) diagnosed hypertension and type 1 or 2 diabetes, (4) history of or current diagnosis of an eating disorder, (5) serious current physical disease (e.g., renal disease or cancer), (6) past bariatric surgery, (7) current or history of substance abuse in the past 6 months, (8) current treatment for a serious psychological disorder (e.g., schizophrenia and bipolar disorder) or (9) contraindications to walking. Consented women will become not eligible to participate in the study if they are not randomized by 16-week 6 days gestation (see D. Detailed Study Procedure: Recruitment and enrollment)—this is because the study intervention starts ≤ 17 weeks gestation. Also, women will become not ineligible for participation if they did not complete the baseline data (T1): online survey via REDCap, two 24-hour dietary recall and wear the Actigraph monitor for at least 4 consecutive days with 6 hours per day.

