Sample size/power. Our primary outcome variable is weekly gestational weight gain (GWG). A final sample size of 72 women (36 per group, after accounting for 20% attrition from the 90 enrolled) will have 80% power to detect a time-averaged between-group difference in weekly GWG with a medium effect size (standardized between-group difference of 0.6). This effect size is translated to a between-group difference of 0.33 lb in weekly GWG, assuming a common standard deviation of 0.55 lb (or 0.25 kg) based on previous research.²⁷ The power analysis was conducted using mixed-effect linear modeling with a two-sided significance level of 0.05, assuming a correlation of 0.7 between the two weekly GWG measures. Due to the pilot nature of the study, our sample size is not powered to detect smaller effect sizes (<0.6). Nevertheless, we will report point estimates, effect sizes, and 95% confidence intervals. These estimates along with clinical significance will guide the results interpretation and sample size determination for a future full-scale RCT (R01).

C. Measurement/ Instrumentation

All participants will be assessed at ≤ 16 week-gestation (T1), 24-27 week-gestation (T2) and 35-37 week-gestation (T3). Survey data will be collected online using password-protected security-ensured Research Electronic Data Capture (REDCap), a secure web application for building and managing online surveys and databases. Primary and secondary outcomes will be extracted from electronic health record. An incentive of \$40 will be provided for participation in each point of data collection for all measurements.

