First zoom meeting (information session lead by research staff). Participants will use their personal devise, for example, computer or smartphone to join the zoom meeting, which will take up to 60 minutes. *First*, the trained research staff will ask participants if they have questions and answer questions accordingly. Next, they will review key summary of incentive and intervention requirements (using "share" function in zoom) with the participants and answer questions that they may have. Also, research staff will ask

the potential participants to think through their current and anticipated responsibilities and life situations before providing verbal consent for participation. After that, the research assistant will electronic consent via REDCap follow by showing them how to complete data collection activities (online survey, 24 hour-dietary recall and Actigraph) and requirements. Then, participants will be asked to self-generate reminders to complete data collection activities. Finally, participants will be informed about the purpose of the second zoom meeting. They will also be informed that participants who complete all data collection activities must join the second zoom meeting by 16 weeks and 6 days gestation. Otherwise, they will become not eligible to participate in the study. This is because our intervention must start at or prior to 17 weeks gestation.

Second zoom meeting (either audio or video recorded per participant preferences): **Randomization**.

Participants will be randomly assigned to an intervention or usual care group (1:1 ratio).

Usual care group. We will thank women in the usual care group and end the zoom meeting.

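### Aims 3 and 4: the change-from-baseline contrast is valid, but the model does not adjust for the T1 value of the outcome and so gives up precision

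*Combined protocol and SAP*

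**What the plan says.** Section F (Statistical analysis) models each continuous outcome of Aims 3 and 4 "as a linear function of treatment, time, and the treatment by time interaction". Diet, physical activity and psychological eating fall under Aim 3, and motivation, emotion and cognition under Aim 4. The effect measure follows: "The intervention effects will be estimated by between-group comparisons of change in the outcome (e.g., healthy lifestyle behaviors) from baseline". On adjustment, the plan adds: "Again, we will adjust for within-subject clustering from repeated measures and covariates (e.g., race) in the mixed-effects regression models". Race is the only covariate named.

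Two places fix the timing of T1. The exclusion criteria in section B deal with eligibility "if they did not complete the baseline data (T1): online survey via REDCap, two 24-hour dietary recall and wear the Actigraph monitor". Section D, under the first zoom meeting, says that "participants who complete all data collection activities must join the second zoom meeting by 16 weeks and 6 days gestation". Randomization takes place at that second meeting.

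For numbers, the sample size paragraph in section B gives "A final sample size of 72 women (36 per group, after accounting for 20% attrition from the 90 enrolled"). The objectives present these aims as exploratory, for example "To investigate the potential intervention effects on motivation". No power figure or correlation is given for any Aim 3 or Aim 4 outcome.

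**The concern.** With T1 among the responses and a free treatment term at T1, the treatment-by-time contrast at T3 compares mean changes. It treats the T1 difference between arms as unknown and removes all of it. Since T1 precedes allocation, the expected T1 difference is zero, and any observed difference is chance. Only part of that chance difference, in proportion to the correlation, carries over to follow-up. Subtracting the whole of it over-corrects.

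Aims 3 and 4 carry no power claim, so what they produce is effect estimates and confidence intervals to inform a later trial. As written, those intervals are wider than the data already collected would allow, and a chance T1 imbalance moves the estimates more than it needs to.

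**Working it through.** **The plan's own figure.** The only power statement concerns weekly gestational weight gain (Aim 2): 36 per group, difference 0.33 lb, SD 0.55 lb, correlation 0.7, two-sided 0.05. The SD of the average of two measures is 0.55 × √((1 + 0.7)/2) = 0.507. The standard error is 0.507 × √(2/36) = 0.1195, and 0.33/0.1195 = 2.76. Power is Φ(2.76 − 1.96) = 78.8%, close to the stated 80%. The point made here does not touch that figure.

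**Inputs for Aims 3 and 4.** From the plan: three visits, 1:1 allocation, 90 enrolled (45 per arm) and 72 final (36 per arm). Assumed: SD 1 at every visit, and the same correlation ρ between any two visits, at 0.3, 0.5, 0.7, 0.8 and 0.9. The 0.7 in the sample size paragraph is for two weight-gain rates, so it is not evidence for diet, activity or survey scores. Time is taken as a three-level factor.

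**Formulas.** Let n₁ be the number per arm at T1, with 36 per arm at T2 and T3. The variance of the T3 effect is:

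- as written (free T1 means): 2 × [(1 − ρ²)/36 + (1 − ρ)²/n₁]
- common T1 mean: 2 × (1 − ρ²)/36

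Example at ρ = 0.5 and n₁ = 45. As written: 2 × (0.75/36 + 0.25/45) = 0.0528, SE 0.230. Common T1 mean: 2 × 0.75/36 = 0.0417, SE 0.204. The variance ratio is 0.0528/0.0417 = 1.27.

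A generalized least squares calculation with all three visits gives the same standard errors. The detectable effect is 2.80 × SE (two-sided 0.05, 80% power).

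| ρ | SE as written, n₁ = 45 | SE as written, n₁ = 36 | SE common T1 mean | Variance ratio (45; 36) | Detectable effect in SD, as written (45; 36) | Detectable effect in SD, common T1 mean |
|---|---|---|---|---|---|---|
| 0.3 | 0.269 | 0.279 | 0.225 | 1.43; 1.54 | 0.75; 0.78 | 0.63 |
| 0.5 | 0.230 | 0.236 | 0.204 | 1.27; 1.33 | 0.64; 0.66 | 0.57 |
| 0.7 | 0.180 | 0.183 | 0.168 | 1.14; 1.18 | 0.50; 0.51 | 0.47 |
| 0.8 | 0.148 | 0.149 | 0.141 | 1.09; 1.11 | 0.41; 0.42 | 0.40 |
| 0.9 | 0.105 | 0.105 | 0.103 | 1.04; 1.05 | 0.29; 0.30 | 0.29 |

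With 36 per arm throughout, the ratio reduces to 2/(1 + ρ). To match a baseline-adjusted analysis of 36 per arm, the change contrast would need 36 × 2/(1 + ρ) per arm: about 55, 48, 42 and 40 at ρ = 0.3, 0.5, 0.7 and 0.8.

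**Simulation.** In 20,000 null trials at each of ρ = 0.3, 0.5 and 0.7 (36 per arm), both analyses were unbiased with type I error near 5%. The variance ratios were 1.52, 1.29 and 1.16. These lie slightly below theory (1.54, 1.33, 1.18), as expected when the T1 slope has to be estimated.

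**Chance imbalance.** With complete cases, a T1 difference of d shifts the expected change contrast by −(1 − ρ)d. One standard error of a T1 difference is √(2/45) = 0.21 SD or √(2/36) = 0.24 SD. An imbalance of 0.2 SD therefore shifts the contrast by 0.14, 0.10, 0.06 or 0.04 SD at ρ = 0.3, 0.5, 0.7 or 0.8.

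**The case against.** **The covariate list is open, so T1 adjustment may be intended.** The plan does not exclude it. But adding the T1 value to the written model would not help. A covariate that is constant over time adds the same amount to a woman's T1 and T3 values and cancels from the change. In a simulated complete data set (36 per arm, ρ = 0.5), the T3 interaction estimate and its standard error were the same to three decimals with no covariate, with race, and with race plus the T1 value. The gain needs a different model structure or response set, and the plan states neither.

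**The analysis is legitimate and the aims are exploratory.** Both statements are true. Nothing is biased, and valid intervals that are somewhat wide mislead no one. This limits the weight of the point. It does not justify the lost precision, since the data are in hand.

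**The size of the loss is not known.** This stands. At a correlation of 0.9 the loss is negligible. The equal-SD assumption also matters. Let k be the T1 SD divided by the T3 SD. With 36 per arm and ρ = 0.7, the ratio is (1 + k² − 1.4k)/0.51, which gives 1.02 at k = 0.8, 1.18 at k = 1 and 1.59 at k = 1.25. The loss can therefore be almost nil or larger than tabulated. Apart from the small cost of estimating one slope, baseline adjustment does not do worse.

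**The eligibility sentence is garbled.** The exclusion criteria use a double negative for women with incomplete T1 data. The first zoom meeting text is clear, and it establishes on its own that T1 comes before randomization.

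**Conclusion.** The concern holds. As written, the Aims 3 and 4 effect is an unbiased change-score comparison that makes inefficient use of a pre-randomization baseline. Under equal SDs and equal correlations between visits, the variance is inflated by 9% to 43% for correlations from 0.8 down to 0.3 (45 per arm at T1, 36 later). With 36 per arm throughout, the range is 11% to 54%. The correlation is an assumption, and the true loss could be close to zero for a highly stable measure. The point is about precision only: it leaves the Aim 2 sample size and every stated power figure unchanged. It merits a change because the remedy uses data that each woman must supply before she can be randomized.

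**What to change.** In section F, for Aims 3 and 4, specify one of these two models:

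- Keep T1, T2 and T3 as responses, with time as a three-level factor, and constrain the arms to a common T1 mean. That means dropping the treatment main effect and keeping time, treatment by T2, treatment by T3, race and the other covariates. The three-level coding is what allows the constraint to be placed at T1.
- Model T2 and T3 only, with the T1 value of the same outcome as a covariate, along with race and the other covariates.

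Use one or the other, not both together. Report the treatment terms at T2 and T3 as the intervention effects, with 95% confidence intervals. The cost is one or two sentences, best added before outcome data are examined. No extra data, visits or participants are needed.
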